#### **7.1.5.3.4 Survival Follow-up Visits**

Subjects, who experience confirmed disease progression or start a new anti-cancer therapy, will move into the Survival Follow-Up Phase and should be contacted by telephone every 12 weeks to assess for survival status until death, withdrawal of consent, or the end of the study, whichever occurs first.

The Sponsor may request survival status be assessed at additional time points during the course of the study. For example, these additional time points may be requested prior to an efficacy interim analysis, and/or final analysis. All subjects who are not known to have died prior to the request for these additional survival status time points will be contacted at that time.

When a subject discontinues trial treatment in treatment period and/or retreatment period, procedures for discontinuation will be conducted.

## **7.2 Assessing and Recording Adverse Events**

An adverse event is defined as any untoward medical occurrence in a patient or clinical investigation subject administered a pharmaceutical product and which does not necessarily have to have a causal relationship with this treatment. An adverse event can therefore be any unfavourable and unintended sign (including an abnormal laboratory finding, for example), symptom, or disease temporally associated with the use of a medicinal product or protocol-specified procedure, whether or not considered related to the medicinal product or protocol-specified procedure. Any worsening (i.e., any clinically significant adverse change in frequency and/or intensity) of a preexisting condition that is temporally associated with the use of the Sponsor's product, is also an adverse event.

Changes resulting from normal growth and development that do not vary significantly in frequency or severity from expected levels are not to be considered adverse events. Examples of this may include, but are not limited to, teething, typical crying in infants and children and onset of menses or menopause occurring at a physiologically appropriate time.

Sponsor's product includes any pharmaceutical product, biological product, device, diagnostic agent or protocol-specified procedure, whether investigational (including placebo or active comparator medication) or marketed, manufactured by, licensed by, provided by or distributed by the Sponsor for human use.

Adverse events may occur during clinical trials, or as prescribed in clinical practice, from overdose (whether accidental or intentional), from abuse and from withdrawal.

Progression of the cancer under study is not considered an adverse event.

All adverse events that occur after the consent form is signed but before treatment allocation/randomization must be reported by the investigator if they cause the subject to be excluded from the trial, or are the result of a protocol-specified intervention, including but not limited to washout or discontinuation of usual therapy, diet, placebo treatment or a procedure. From the time of treatment allocation/randomization through 90 days following cessation of treatment, or 30 days following cessation of trial treatment if the subject initiates new anticancer therapy, whichever is earlier, all adverse events must be reported by the investigator. Such events will be recorded at each examination on the Adverse Event case report forms/worksheets. The reporting timeframe for adverse events meeting any serious criteria is described in section 7.2.3.1. The investigator will make every attempt to follow all subjects with non-serious adverse events for outcome.

Electronic reporting procedures can be found in the Electronic Data Capture (EDC) data entry guidelines. Paper reporting procedures can be found in the Investigator Trial File Binder (or equivalent).

Adverse events will not be collected for subjects during the pre-screening period (for determination of archival tissue status) as long as that subject has not undergone any protocol-specified procedure or intervention. If the subject requires a blood draw, fresh tumor biopsy etc., the subject is first required to provide consent to the main study and AEs will be captured according to guidelines for standard AE reporting.

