Duration of Participation	
Each subject will participate in the trial for up to 28 months from the time the subject signs the informed consent form (ICF) through the final protocol-specified contact.
 
After a screening phase of up to 28 days, each subject will be receiving assigned treatment for up to 24 months. After treatment discontinuation, subjects will be monitored for adverse events (AEs) and serious adverse events (SAEs) for 90 days. Subjects who initiate new anticancer therapy less than 30 days after study treatment discontinuation will be monitored for AEs/SAEs for 30 days. Subjects who initiate new anticancer therapy between 30 days and 90 days after study treatment discontinuation will be monitored for AEs/SAEs until the day new anticancer therapy is initiated. Subjects will be treated until progressive disease, unacceptable toxicity, intercurrent illness that prevents further administration of treatment, investigator's decision to withdraw treatment, subject withdrawal of consent, pregnancy of the subject, noncompliance with trial treatment or procedure requirements, subject completes treatment, or administrative reasons requiring cessation of treatment, at which point they will be discontinued from the study. Upon disease progression, subjects in the monotherapy arm will be able to cross-over to the combination regimen.

Randomization Ratio	N/A

A list of abbreviations used in this document can be found in Section 12.6.

Preladenant will be used throughout the protocol to refer to MK-3814 as supplied by the Sponsor.

Pembrolizumab will be used throughout the protocol to refer to KEYTRUDA® or MK-3475 as supplied by the Sponsor.

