### 3.1 Primary Objective(s) & Hypothesis(es)

- (1) To evaluate the safety and tolerability of dose level-specific preladenant in monotherapy (Part 1) and in combination with pembrolizumab (Parts 1 and 2)

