## 6.0 TRIAL FLOW CHART

### 6.1 Flowchart

Preladenant in Monotherapy (Arm 1 ; Part 1)												
	Screening	Treatment Phase						Tumor Assessment	End of Treatment	Post-treatment Follow-Up Phase		
		Cycle 1			Cycle 2-4		Cycles 5 and all Subsequent Cycles	Every 9 weeks	Discontinuation	Safety Follow-up		Survival Follow-Up 
		Day 1	Day 8	Day 15	Day 1	Day 15	Day 1		At Treatment Discontinuation	30 days after the last dose	90 days after the last dose	Every 12 weeks post discontinuation
Scheduling Window (Days) 	-28 to -1	+3	±3	±3	±3	±3	±3	±7		+7	+7	±7
Administrative Procedures												
Informed Consent 	X											
Informed Consent for Optional Future Biomedical Research 	X											
Inclusion/Exclusion Criteria 	X											
Subject Identification Card 	X											
Medical History 	X											
Prior Oncology Treatment History 	X											
Prior Medications 	X											
Concomitant Medications 	X	X	X	X	X	X	X		X	X		
Clinic Procedures/Assessments												
Physical Examination 	X	X			X		X		X 	X		
12-Lead Electrocardiogram 	X											
Vital Signs 	X	X	X	X	X		X		X	X		
ECOG Performance Status 	X	X			X		X		X	X		
Dispense preladenant 		X			X		X					
Adverse Events Reporting 	X	X	X	X	X	X	X		X	X	X	

Preladenant in Monotherapy (Arm 1 ; Part 1)												
	Screening	Treatment Phase						Tumor Assessment	End of Treatment	Post-treatment Follow-Up Phase		
		Cycle 1			Cycle 2-4		Cycles 5 and all Subsequent Cycles	Every 9 weeks	Discontinuation	Safety Follow-up		Survival Follow-Up 
		Day 1	Day 8	Day 15	Day 1	Day 15	Day 1		At Treatment Discontinuation	30 days after the last dose	90 days after the last dose	Every 12 weeks post discontinuation
Scheduling Window (Days) 	-28 to -1	+3	±3	±3	±3	±3	±3	±7		+7	+7	±7
Tumor Imaging and RECIST 1.1 Response Assessment 	X							X	X			
Survival Status 												X
Laboratory Procedures/Assessments												
Archival or Newly Obtained Tumor Tissue Collection for Biomarker Analysis and Molecular Profiling 	X											
Blood for Genetic Analyses 		X										
Hematology 	X	X	X	X	X	X	X		X	X		
Blood for RNA Analyses 		X			X		X		X			

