9. Adverse events and serious adverse events will be recorded from the time of treatment allocation. All adverse events and serious adverse events that occur after the consent form is signed but before treatment allocation must be reported by the Investigator if they cause the subject to be excluded from the trial, or are the result of a protocol-specified intervention, including but not limited to washout or discontinuation of usual therapy or a study procedure. After treatment discontinuation, each subject will be followed for 90 days for adverse event and serious adverse event monitoring, 30 days if the subject initiates new anticancer therapy less than 30 days after study treatment discontinuation, or the day new anticancer therapy is initiated if between 30 days and 90 days after study treatment discontinuation. Subjects with an ongoing AE of Grade >1 at the time of treatment discontinuation will be followed until resolution of the AE to Grade 0-1, until considered stable by the treating physician, or until beginning a new anticancer therapy, whichever occurs first.
10. Baseline radiology images by CT (or MRI) of chest, abdomen, and pelvis, and all known tumor sites (if evaluable by imaging) must be obtained within 28 days prior to C1D1 and must be repeated every 9 weeks ( $\pm 7$  days) from C1D1 (See SIM). Imaging must be obtained at the End of Treatment visit at discontinuation unless done within the previous 4 weeks. Images are to be submitted to the central imaging vendor for potential future central analysis.
11. After confirmed disease progression subjects will be contacted by telephone every 12 weeks for survival until withdrawal of consent to participate in the study, becoming lost to follow-up, death, or end of the study, whichever occurs first.
12. Tumor tissue (archival or newly obtained biopsy) will be required at Screening upon signing the informed consent for the study. This sample will be assessed to collect information on biomarkers for all subjects enrolled in the study. Tumor tissue will be sent to central laboratory for biomarker analysis and leftover tissue may be saved for future biomedical research (FBR) if the subject signs the FBR consent.

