### **7.2.3 Immediate Reporting of Adverse Events to the Sponsor**

#### **7.2.3.1 Serious Adverse Events**

A serious adverse event is any adverse event occurring at any dose or during any use of Sponsor's product that:

- Results in death;
- Is life threatening;
- Results in persistent or significant disability/incapacity;
- Results in or prolongs an existing inpatient hospitalization;
- Is a congenital anomaly/birth defect;
- Is an other important medical event.

**Note:** In addition to the above criteria, adverse events meeting either of the below criteria, although not serious per ICH definition, are reportable to the Sponsor in the same timeframe as SAEs to meet certain local requirements. Therefore, these events are considered serious by the Sponsor for collection purposes.

- Is a new cancer (that is not a condition of the study);
- Is associated with an overdose.

Refer to [Table 14](#) for additional details regarding each of the above criteria.

For the time period beginning when the consent form is signed until treatment allocation/randomization, any serious adverse event, or follow up to a serious adverse event, including death due to any cause other than progression of the cancer under study (reference Section 7.2.3.3 for additional details), that occurs to any subject must be reported within 24 hours to the Sponsor if it causes the subject to be excluded from the trial, or is the result of a protocol-specified intervention, including but not limited to washout or discontinuation of usual therapy, diet, placebo treatment or a procedure.

For the time period beginning at treatment allocation/randomization through 90 days following cessation of trial treatment, or 30 days following cessation of trial treatment if the subject initiates new anticancer therapy, whichever is earlier, any serious adverse event, or follow up to a serious adverse event, including death due to any cause other than progression of the cancer under study (reference Section 7.2.3.3 for additional details), whether or not related to the Sponsor's product, must be reported within 24 hours to the Sponsor either by electronic media or paper. Electronic reporting procedures can be found in the EDC data entry guidelines. Paper reporting procedures can be found in the Investigator Trial File Binder (or equivalent).

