Additionally, any serious adverse event, considered by an investigator who is a qualified physician to be related to the Sponsor's product that is brought to the attention of the investigator at any time following consent through the end of the specified safety follow-up period specified in the paragraph above, or at any time outside of the time period specified in the previous paragraph also must be reported immediately to the Sponsor.

All subjects with serious adverse events must be followed up for outcome.

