### **8.6.2 Statistical Methods for Safety Analyses**

Safety and tolerability will be assessed by clinical review of all relevant parameters including AEs, SAEs, laboratory tests, vital signs, ECG measurements, and physical examinations.

Adverse events will be summarized by counts and frequencies for each dose level and treatment arm. Patients enrolled in Part 1 in the combination arm (Arm 2) and treated at the same dose level as that selected for Part 2, will also be pooled together with patients enrolled in Part 2 for safety analysis if they have the same tumor type. Laboratory tests, vital signs, and other safety endpoints will be summarized as appropriate.

Dose limiting toxicities will be listed, and further summarized by dose level and treatment arm. The pool adjacent-violators-algorithm [22], which forces the DLT rate estimates to be non-decreasing with dose levels and pools adjacent violators for weighted estimates by sample size, will be used to estimate the DLT rates across doses in each treatment arm. The estimates of the DLT rates among subjects treated at the MTDs (or MADs) and the 80% Bayesian credible intervals based on a prior distribution of Beta (1,1) for the estimates will be provided.

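### The post-treatment AE/SAE window has two conflicting definitions when new anticancer therapy starts after Day 30 and up to Day 90

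*Combined protocol and SAP*

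**What the plan says.** Two rules stand in the current text.

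**Three-case rule.** Section 1.0 (Duration of Participation), Section 2.1 and Section 7.1.5.3.2 use the same sentences. The default is 90 days after discontinuation. It becomes 30 days if new anticancer therapy begins before Day 30. For a later start, "Subjects who initiate new anticancer therapy between 30 days and 90 days after study treatment discontinuation will be monitored for AEs/SAEs until the day" the new therapy begins. Section 6.1 repeats this in footnote 9 (Arm 1 chart) and footnote 10 (Arm 2 chart), where the third case reads "or the day new anticancer therapy is initiated if between 30 days and 90 days after study treatment discontinuation". Both footnotes are attached to the row labelled "Adverse Events Reporting".

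**Two-case rule.** Section 7.2 covers all adverse events: 90 days, "or 30 days following cessation of trial treatment if the subject initiates new anticancer therapy, whichever is earlier, all adverse events must be reported". Section 7.2.3.1 repeats the construction for the 24-hour SAE duty: "or 30 days following cessation of trial treatment if the subject initiates new anticancer therapy, whichever is earlier, any serious adverse event". Neither has a case for therapy that begins between Day 30 and Day 90.

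Section 7.2.3.1 adds that SAEs judged related to the product and learned of during the follow-up period, "or at any time outside of the time period specified in the previous paragraph also must be reported immediately to the Sponsor".

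**The concern.** Sites can follow either text. Section 7.2 is the one that says what must be reported, and a site applying it literally would leave out events from Day 31 up to the start of new therapy. A site working from the flow chart would include them. Two subjects with identical histories could then contribute different data.

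This matters because safety and tolerability are the primary objective (Section 3.1). The analysis plan does not settle it: Section 8.6.2 says "Adverse events will be summarized by counts and frequencies for each dose level and treatment arm" but gives no post-treatment cut-off. Dose levels are small, with 3 to 14 subjects each (Section 5.2.1.2), so a few events included or excluded can visibly change a frequency.

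The 7.2 rule is also awkward to operate. Until new therapy begins, the 90-day duty applies. The shorter cut-off can be applied only afterwards, by closing at Day 30 a window in which later events may already have been recorded.

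**Working it through.** The plan states no figure to reproduce; the check compares the two rules case by case.

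**Inputs**
- Three-case rule: Sections 1.0, 2.1, 6.1 (footnotes 9 and 10) and 7.1.5.3.2.
- Two-case rule: Section 7.2 (all AEs) and Section 7.2.3.1 (SAEs).
- Let t be the day, counted from treatment discontinuation, on which new anticancer therapy begins. Discontinuation and cessation of treatment are taken as the same day.

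**End of window**
- Three-case rule: Day 30 if t < 30; Day t if 30 ≤ t ≤ 90; Day 90 if no new therapy by then.
- Two-case rule, read literally: the earlier of Day 90 and Day 30, so Day 30 whenever new therapy begins by Day 90; Day 90 if none.
- Two-case rule, read narrowly (30-day clause applies only to therapy begun within 30 days): Day 30 if t ≤ 30; otherwise Day 90.

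**Gaps for 30 < t ≤ 90**
- Literal reading: t - 30 days, with 7.2 the shorter window.
- Narrow reading: 90 - t days, with 7.2 the longer window.

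| New therapy begins | Three-case end | 7.2 literal end | Gap | 7.2 narrow end | Gap |
|---|---|---|---|---|---|
| Day 20 | 30 | 30 | 0 | 30 | 0 |
| Day 30 | 30 | 30 | 0 | 30 | 0 |
| Day 31 | 31 | 30 | 1 | 90 | 59 |
| Day 45 | 45 | 30 | 15 | 90 | 45 |
| Day 60 | 60 | 30 | 30 | 90 | 30 |
| Day 75 | 75 | 30 | 45 | 90 | 15 |
| Day 90 | 90 | 30 | 60 | 90 | 0 |
| None by Day 90 | 90 | 90 | 0 | 90 | 0 |

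The rules agree for a start up to Day 30 and when there is no new therapy. Read literally, they disagree for every start from Day 31 to Day 90. Read narrowly, they disagree for every start from Day 31 to Day 89. Neither reading reconciles them.

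**Could the two rules serve different purposes?** One might say that the three-case rule governs monitoring and the two-case rule reporting. The flow charts rule this out, because footnotes 9 and 10 hang on the adverse event reporting row.

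**Which data are exposed?**
- Product-related SAEs: not exposed; reportable at any time (7.2.3.1).
- Other SAEs known before new therapy begins: already due within 24 hours. Only those learned of later are exposed.
- Grade >1 events ongoing at discontinuation: followed under either rule (2.1, 6.1, 7.1.5.3.2).
- DLTs: not exposed; observed on Days 1 to 21 of Cycle 1 (5.2.2).
- New-onset non-serious events after Day 30: exposed. Section 7.2 has them recorded at each examination, and both flow charts schedule adverse event contacts at 30 and 90 days after the last dose with none between, although 7.1.2.1 allows more frequent assessment if clinically indicated. An event on Day 45 may first come to light at the 90-day contact. If new therapy began on Day 60, the flow-chart footnotes include that event and the literal text of 7.2 does not.

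The documents give no rate of new therapy after discontinuation, so the share of subjects affected cannot be computed and none is assumed.

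**The case against.** The best case on the other side concedes the mismatch and argues that little follows from it.

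- **Loss of data is not certain.** On the narrow reading, 7.2 would collect more than the three-case rule. This stands as a limit: the direction and size of the gap depend on the reading. It does not restore agreement.
- **Events are reportable when they occur.** Before new therapy begins the 90-day duty is in force, so most SAEs would already have been sent. This stands for SAEs. It is weaker for non-serious events, which are recorded at examinations, with none scheduled between the two contacts.
- **Section 7.1.5.3.2 may reach further than it seems.** Its follow-up sentence for Grade >1 events, unlike Sections 2.1 and 6.1, is not confined to events ongoing at discontinuation. It may therefore cover some that arise after Day 30. This narrows the exposed data further, but leaves Grade 1 events and does not settle the reporting window.
- **Rewording does not secure the data.** For a start before Day 90, the 90-day contact falls after the corrected window has closed, and the subject has moved to survival follow-up (7.1.1.6.2, 7.1.5.3.4). This is fair: the edit settles which events count, not how they are elicited.
- **Other material may settle it.** Data entry guidelines and the trial file binder are cited but not supplied. They could align practice across sites. They would not change the protocol's stated duty.

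**Conclusion.** The inconsistency is real and lies in current operative text. For a start of new anticancer therapy on Day 31 to Day 90, Sections 7.2 and 7.2.3.1 read literally close the window 1 to 60 days before Sections 1.0, 2.1, 6.1 and 7.1.5.3.2 do. On the narrow reading they close it up to 59 days after. No reading makes the two rules agree across that range.

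The consequence is bounded. It falls on the AE and SAE summaries that serve the primary safety objective, mainly through new-onset non-serious events and SAEs not judged related that become known late. The DLT endpoint is untouched, and no test or sample size depends on the window. The number of subjects affected is unknown. The correction should be made: the conflict is in the text that defines the investigator's reporting duty, and it is easily removed.

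**What to change.** Replace the window wording in the reporting paragraph of Section 7.2 and in the post-allocation paragraph of Section 7.2.3.1 with the three cases already used elsewhere in the protocol: 90 days after discontinuation; 30 days if new anticancer therapy begins before Day 30; the day it begins if that falls between Day 30 and Day 90. Leave the paragraph on product-related SAEs in 7.2.3.1 unchanged.

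The cost is the rewording of two paragraphs. No visit is added, since the 90-day adverse event contact is already in both flow charts. Sites should understand that the window is defined by when the event occurred, so an event that arose before new therapy began still counts if first reported at a later contact.

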### **7.2.1 Definition of an Overdose for This Protocol and Reporting of Overdose to the Sponsor**

For this trial, an overdose of preladenant will be defined as any dose exceeding the prescribed dose for preladenant by  $\geq 20\%$  of the indicated dose. An overdose of pembrolizumab will be defined as any dose of 1000 mg or greater ( $\geq 5$  times the indicated dose).

No specific information is available on the treatment of overdose of preladenant or pembrolizumab. In the event of overdose, the subject should be observed closely for signs of toxicity. Appropriate supportive treatment should be provided if clinically indicated.

If an adverse event(s) is associated with (“results from”) the overdose of Sponsor's product or vaccine, the adverse event(s) is reported as a serious adverse event, even if no other seriousness criteria are met.

If a dose of Sponsor's product or vaccine meeting the protocol definition of overdose is taken without any associated clinical symptoms or abnormal laboratory results, the overdose is reported as a non-serious Event of Clinical Interest (ECI), using the terminology “accidental or intentional overdose without adverse effect.”

All reports of overdose with and without an adverse event must be reported by the investigator within 24 hours to the Sponsor either by electronic media or paper. Electronic reporting procedures can be found in the EDC data entry guidelines. Paper reporting procedures can be found in the Investigator Trial File Binder (or equivalent).

